Subject exit information to be collected include the following questions,

- Date of Subject Exit.
- Reason for Subject Exit (End of Follow Up period (30 days) / Subject Withdrawn Non-compliance / Subject Withdrawn Adverse Event / Subject Withdrawn Subject's own request / Subject Withdrawn Lost to follow-up / Investigator Decision / Other (Specify)).
- Complete of POSAS and exit questionnaire.

9.3 PICO 14 DEVICE RETURN.

All PICO 14 pumps will be returned to S&N for download of the in-built data chip. Once the pumps have been removed from the subject they are to be decontaminated using the following procedure:

- Label a zip-locked bag with subject ID number, initials and date labelled.
- At the Treatment Discontinuation Assessment the PICO dressing will be removed from the subject in order to inspect the surgical site as per the study protocol.
- The PICO dressing will be disconnected from the pump and the dressing disposed of as clinical waste.
- The surface of the pump should be wiped with a disinfectant wipe. Remove and retain the batteries. Clean the batteries and the inside of the battery compartment with a disinfectant wipe.

CONFIDENTIAL AND PROPRIETARY

Study Protocol—Device	Smith-Nephew
and performance of PICO 14 in the	Number: PICO14.WND.PRO.2019.03
	Version: 2.0, 12Sep2021 Page: Page 74 of 131

- Put the PICO pump and the batteries in the labelled bag.
- During the monitoring visits, the study monitor will count the devices and verify that they have been labelled correctly, collect devices and shipment will be arranged to Smith+Nephew Wound Management, Hull, UK.

In an identified handling area at Smith+Nephew Wound Management, Hull, UK, the devices shall be processed to have their internal memory contents downloaded, analysed and saved following an approved NPD (New Product Development) Work Instruction.

9.4 HEALTH ECONOMICS/QUALITY OF LIFE.

No Quality of Life Questionnaires will be collected for this study however, assessment of acceptability of the therapy will be made by specific targeted questions to the clinician and subject as described in section 9.2.5 above.

9.5 SCAR QUALITY ASSESSMENT (AT DAY 0, DAY 14 AND AT EXIT VISIT).

The Patient and Observer Scar Assessment Scale (POSAS) is a comprehensive scale that is designed for the evaluation of all types of scars by professionals and patients. The POSAS aims to measure scar quality. The Patient Scale gives the POSAS an important extra dimension because the patient's opinion is mandatory for a complete scar evaluation. The Observer Scale will be completed by an independent member of the study team.

The POSAS consists of two parts: a Patient Scale and an Observer Scale. Both scales contain six items that are scored numerically and make up a 'Total Score' of the Patient and Observer Scale. The sum altogether will give the 'Total Score' of the POSAS. Besides the 10-step scale, category boxes are available to score nominal parameters (e.g. type of colour). Moreover, the patient and observer also score their 'Overall Opinion'.

Each item of both scales has a 10-point score, with 10 indicating the worst imaginable scar or sensation. The lowest score is '1', and corresponds to the situation of normal skin (normal pigmentation, no itching etc.), and goes up to the worst imaginable. The Total Score of both scales can be simply calculated by summing up the scores of each of the six items. The Total Score will therefore range from 6 to 60. Besides the six items the 'Overall Opinion' of the scar quality is scored separately of both patients and observers.

A full description of the Patient and Observer Scar Assessment Scale can be found in appendix 22.5.

CONFIDENTIAL AND PROPRIETARY

Study Protocol—Device	Smith-Nephew
and performance of PICO 14 in the	Number: PICO14.WND.PRO.2019.03
	Version: 2.0, 12Sep2021
	Page: Page 75 of 131

10. STUDY PROCEDURES- CHRONIC WOUNDS AND DEHISCHED SURGICAL WOUNDS ONLY.

10.1 VISITS AND EXAMINATIONS.

10.1.1 SUMMARY.

For a summary of the required procedures by visit, refer to the Study Schematic Table 10.1-1: Study Procedures by Visit.

Table 10.1-1: Study Procedures by Visit- Chronic wounds and dehisced surgical wounds ONLY.

CONFIDENTIAL AND PROPRIETARY

Study Protocol—Device	Smith-Nephew
and performance of PICO 14 in the	Number: PICO14.WND.PRO.2019.03
	Version: 2.0, 12Sep2021
	Page: Page 76 of 131

Schedule of events	Pre- Treatment Data	Treatmen t Data DAY 0	DAY 7 Visit (-3 days)	DAY 14 Visit (-2 days)	Day 21 Visit (-3 days)	End of therapy and Exit visit DAY 28 (-3 days)	Additional dressing change (Day 1-27)	Unscheduled Visit or Early Exit
Informed Consent		Х						
Inclusion/Exclusion	Х	х						
Demographics/ Medical History	Х	Х						
Wound Assessment (including measurement)		х	Х	Х	Х	Х		Х
Dressing assessment			Х	Х	Х		Х	X
Complications assessment		х	Х	Х	X	Х	Х	X
Photographic assessment		Х	Х	Х	Х	Х	Х	Х
Treatment Data Collection		х	Х	Х	Х	Х		
Concomitant medication	Х	Х	Х	Х	Х	Х	Х	X
Dressing application		Х	Х	X	X	Return to standard care	Х	X
Dressing removal Assessment			Х	Х	Х	Х	Х	X
Patient and clinician acceptability questionnaire completion			Х	х	x	X	X	Х
Adverse Event Assessment	Х	Х	Х	Х	Х	Х	Х	Х
Device Deficiency Assessment		Х	Х	Х	Х		Х	Х
End of Study/Exit						Х		Х

CONFIDENTIAL AND PROPRIETARY

Study Protocol—Device	Smith-Nephew
	Number: PICO14.WND.PRO.2019.03
	Version: 2.0, 12Sep2021 Page: Page 77 of 131
	Page: Page // Or 131

10.1.2 SCREENING VISIT/BASELINE VISIT.

NOTE: Any subject who signs an informed consent/assent but fails to meet the required entry criteria is considered to be a Screen Failure. Screen Failure subjects will be assigned subject numbers and ONLY the screening visit and their demographic information must be captured in the appropriate CRF with the reason for screen failure specified.

- 1. Obtain written informed consent from the subject as detailed in Section 7.5.
 - ---- Do not proceed until consent has been obtained -----
- Obtain demographic information and medical history, including information on all concomitant medications/therapies.
- 3. Screen the subject against eligibility criteria and assign a study number to the subject (XX.YYY where XX= site number and YYY= subject number at site.
- 4. Instruct the subject on treatment procedures.
- 5. Complete a full wound assessment sections (10.4.2).
- 6. Take a photograph of the reference wound showing the photo label as supplied.
- 7. Product/therapy used prior to study.
- 8. Assess the peri-wound skin.
- 9. Take a photograph of the reference wound showing the photo label as supplied (section 10.4.3).
- Dispense study product. Record pump lot number, size of dressing used and any ancillary products applied (SECURA No-Sting Skin prep, RENASYS Adhesive Gel Patch).
- 11. Take photograph of dressing in place by camera supplied by Sponsor and add label supplied.
- 12. VAS score will be recorded upon product application.
- 13. Assess ease of application, ease of establishing seal/negative pressure delivery, satisfaction of applying IP.

CONFIDENTIAL AND PROPRIETARY

Study Protocol—Device	Smith-Nephew
and performance of PICO 14 in the	Number: PICO14.WND.PRO.2019.03
	Version: 2.0, 12Sep2021
	Page: Page 78 of 131

- 14. If any AE or DevD are observed or reported, they must be recorded as instructed in Section 12, Adverse Events and Device Deficiencies. Take a photograph of the wound/dressing as appropriate.
- 15. Instruct subject of the follow up visit at day 7 (-3 days).

10.1.3 DAY 7 (-3 DAYS) FOLLOW UP DRESSING INSPECTION.

- 1. Record date and treatment setting.
- 2. If therapy has been discontinued prior to this visit or dressing is no longer in place, complete the End of Therapy Assessment (10.1.5below).
- 3. Record if therapy has been interrupted since the previous assessment and how long.
- 4. Record any changes in general health and record the use of concomitant medications.
- 5. Take photograph of dressing in place by camera supplied by Sponsor and add label supplied.
- 6. Dressing removal assessment.
- 7. Assess the peri-wound skin.
- 8. Complete a full Wound Assessment (section 10.4.2).
- 9. Take photograph of the wound site area.
- 10. A new dressing will be applied and the PICO14 pump will be restarted to apply for up to 7 days.
- 11. Take photograph of new dressing in place.
- 12. Assess subject comfort (yes, no) and pain level (Visual Analogue Scale).
- 13. If any adverse device effects or device deficiencies are observed or reported, they must be recorded as instructed in Section 12 Adverse events and device deficiencies. Take a photograph of the wound/dressing as appropriate.
- 14. Instruct the subject on follow-up procedures, including returning to the treatment facility for the Assessment Visit at 14 (-2) days. Record date of assessment.

CONFIDENTIAL AND PROPRIETARY

Study Protocol—Device	Smith-Nephew
and performance of PICO 14 in the	Number: PICO14.WND.PRO.2019.03
	Version: 2.0, 12Sep2021
	Page: Page 79 of 131

10.1.4 ASSESSMENT VISIT DAY 14 (-2) DAYS.

- 1. Record date and treatment setting.
- If therapy is being discontinued prior to 14 days, record reason (e.g. PICO 14 NPWT system removed, treatment interrupted for 48 hours or more, clinician recommends a change in treatment, at the discretion of the Investigator, adverse event, subjects own request, lost to follow-up, other).
- 3. Record reason if dressing is no longer in place (e.g. pain/discomfort from the dressing, patient removed, patient's request, adverse event, no vacuum, pump turned off, exudate management level, other).
- 4. Take photograph of dressing in place.
- If any AE or DevD are observed or reported, they must be recorded as instructed in Section 12, Adverse Events and Device Deficiencies. Take a photograph of the wound/dressing as appropriate.
- Record any changes in general health and the use of concomitant medications.
- 7. Record if therapy has been interrupted since the previous assessment and how long.
- 8. Complete the Dressing Removal Assessment.
- 9. Complete a full Wound Assessment (section 10.4.2).
- 10. Assess the peri-wound skin.
- 11. Assess subject satisfaction (overall performance of dressing, comfort, noise level, discreteness, portability, interference with daily living showering, sleeping, socialising, working).
- 12. Assess clinician and participant acceptability of PICO NPWT system (Overall satisfaction, satisfaction with ability to manage, satisfaction regarding dressing retention, satisfaction as compared to other NPWT devices). Record date of assessment.
- 13. Remove NPWT system and re-apply new PICO 14 device onto same wound.
- 14. Assess ease of removal.

CONFIDENTIAL AND PROPRIETARY

Study Protocol—Device	Smith-Nephew
	Number: PICO14.WND.PRO.2019.03
	Version: 2.0, 12Sep2021 Page: Page 80 of 131

- 15. Record pain score (VAS) and patient comfort since last assessment and pain score on dressing removal.
- 16. Photograph wound area using the camera supplied by the Sponsor.
- 17. Follow procedure for removal, appropriate labelling and storage of pump for return to S&N.
- 18. Dispense study product. Record pump batch number, size of dressing used and any ancillary products applied (SECURA No-Sting Skin prep, RENASYS Adhesive Gel Patch).
- 19. Take photograph of the new dressing in place.
- 20. Assess ease of application of new dressing.
- 21. Instruct the subject on follow-up procedures, including returning to the treatment facility for the Assessment Visit at 21 (-2) days. Record date of assessment.

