CONFIDENTIAL AND PROPRIETARY

Study Protocol—Device	Smith-Nephew
and performance of PICO 14 in the	Number: PICO14.WND.PRO.2019.03
	Version: 2.0, 12Sep2021
	Page: Page 36 of 131

5. OBJECTIVE(S).

5.1 PRIMARY OBJECTIVE.

To assess the functional clinical performance of PICO 14 NPWT system over 14 days therapy through the verification of delivery of negative pressure and wound exudate management.

5.2 SECONDARY OBJECTIVES.

Closed incisions ONLY

To assess clinical efficacy and safety of the PICO 14 NPWT system within 30 days of surgery through:

- Incidence of Surgical Site Infection (SSI) Superficial, deep. [CDC criteria].
- Incidence of Surgical site Complications (SSC) [as applicable: dehiscence (superficial/deep etc.), seroma, necrosis, hematoma, suture abscess].
- Condition of peri-wound skin assessed through visual inspection at 7, 14 and 30 days.
- Any pain experienced by the subject in relation to the PICO 14 system.
- Patient tolerability assessed by level of pain and level of satisfaction.
- Clinician acceptability assessed by ease of application and removal.
- Dressing wear time, dressing change frequency and dressing conformability.
- Scar quality measured by Patient and Observer Scar Assessment Scale (POSAS) score.

Chronic Wounds and dehisced surgical wounds ONLY

To assess clinical efficacy and safety of the PICO 14 NPWT system within 28 days therapy period through:

- Incidence of infection.
- Condition of peri-wound skin assessed through visual inspection at 7, 14, 21 and 28 days.
- Any pain experienced by the subject in relation to the PICO 14 system.

CONFIDENTIAL AND PROPRIETARY

Study Protocol—Device	Smith-Nephew
and performance of PICO 14 in the	Number: PICO14.WND.PRO.2019.03
	Version: 2.0, 12Sep2021
	Page: Page 37 of 131

Wound assessment:

- Appearance of the wound.
- Level of exudate.
- Wound pain.
- Size of wound (percentage reduction in area, depth, and volume).
- Patient tolerability assessed by level of pain and level of satisfaction.
- Clinician acceptability assessed by ease of application and removal.
- Dressing wear time, dressing change frequency and dressing conformability.

5.3 OTHER OBJECTIVES.

No other objectives.

5.4 SAFETY.

To assess Adverse Events and Device Deficiencies.

5.5 CLAIMS.

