8.5 RETENTION PERIOD

All eCRFs will be archived once the study is completed and will kept for a period of no less than five years after the later of the following dates: the date of which the study is terminated or completed or; the date that the records are no longer required supporting marketing applications.

8.6 STUDY ENDPOINTS.

8.6.1 PRIMARY ENDPOINT.

Functional clinical performance of the PICO 14 NPWT system over the treatment period to include:

- Delivery of -80mmHg negative pressure to the wound bed over the treatment period. This
 will be measured by download of the built-in data chip from the PICO 14 devices to collect
 NPWT delivery status.
- Exudate management assessed by no occurrence of exudate leaks during the treatment period resulting, or not, in an unplanned dressing change.

8.6.2 SECONDARY ENDPOINTS.

Closed Incisions Only:

Clinical performance and safety of the PICO 14 NPWT system over a 14 day therapy and 30 day follow-up period to include:

- Scar quality measured by POSAS score at Day 14, and day 30.
- Incidence of Surgical Site Infection (SSI) and incidence of Surgical Site Complication (SSC) within 30 days of surgery [CDC criteria].
- Condition of peri-wound skin assessed through visual inspection at 7, 14 and 30 days.
- Level of pain on application, during wear and at dressing removal assessed by VAS scale over the 14 day treatment period.
- Patient satisfaction during wear assessed over the 14 day period. This includes leakage, feeling of moisture on the skin, odour control, level of protection, comfort and showerproof qualities.
- Ease of application and removal of the PICO 14 dressing.

CONFIDENTIAL AND PROPRIETARY

Study Protocol—Device	Smith-Nephew
and performance of PICO 14 in the	Number: PICO14.WND.PRO.2019.03
	Version: 2.0, 12Sep2021
	Page: Page 55 of 131

- Dressing wear time.
- Dressing conformability
- Dressing change frequency and reason for dressing change.
- Clinician acceptability of PICO 14 system at discontinuation of therapy.
- Patient acceptability of PICO 14 system at discontinuation of therapy.

Chronic wounds and dehisced surgical wounds only:

Clinical performance and safety of the PICO 14 NPWT system over a 28 day therapy and no follow-up period to include:

- Incidence of clinical infection
- Appearance of the wound in terms of, tissue type and amount, exudate type and amount, skin condition surrounding the wound, peripheral tissue edema and induration,

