Women of child-bearing potential are excluded from the study. However, if a woman becomes pregnant during the study, S&N must be contacted immediately once the investigator is made aware of the pregnancy and subject will be withdrawn from study. Pregnancy is not an adverse event; however, complications related to the pregnancy may be reportable as determined on a case-by-case basis. Pregnancy-related information will be collected until the end of the pregnancy

9.2 STUDY METHODS AND MEASUREMENTS.

9.2.1 INCISION CLOSURE AND CDC INCISION ASSESSMENT.

A medically qualified individual who is not deemed to have a vested interest in low reporting of complications and infections at an institutional level will complete incision assessment. This will include i) an assessment of whether the incision is fully closed/epithelialised an assessment of delayed healing, iii) an assessment of infection, dehiscence or other complications.

Incision closure is defined as skin closure (100% closed) without drainage or dressing requirements. Primary or first intention healing occurs when tissue is cleanly incised and re-approximated and healing occurs without complications. Incisional wounds are usually completely sealed in 24-48 hours, with continued healing of the underlying structures within 5-7 days. Delayed wound healing would be defined as an incision that is not closed, or "parts" unhealed, >7 days.

Assessment of incision infection will be completed as specified per the CDC definitions of nosocomial surgical site infections at each of the specified time points to identify whether there is superficial, deep, or organ/space infection at the incision site. Infection is defined as "the presence of one or more of the following criteria; abscess, cellulites, discharge, (serous exudate with inflammation, seropurulent, haemopurulent, pus) delayed healing, discoloration, unexpected pain/tenderness/bridging of the epithelium or soft tissue, abnormal smell, or wound breakdown". This can occur with or without the signs of leukocytosis and fever". Cutting K F et al. ²⁴, (2004).

If dehiscence has occurred, the level of dehiscence will be defined as superficial (involve only separation at skin level) or deep (involve separation of tissues below the skin, may or may not include skin separation).

CONFIDENTIAL AND PROPRIETARY

Study Protocol—Device	Smith-Nephew

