- Bruising site (other-please specify).
- Condition of surrounding skin (Healthy / Fragile / Inflamed / Erythematous / Oedematous / Eczematous / Macerated / Bruising / Dry & Flaky / other).
- Incision closed (healed)? (Yes / No).
 - o If no:
 - Incision dehisced (Yes / No. If yes, superficial / deep / partial / length (cm)).
 - Length/parts unhealed, estimation of length/parts unhealed (cm) (vertical/horizontal).
 - Incision clinically infected (Yes / No. If yes, deep or superficial infection).
- Clinical signs of infection (none / increased exudate-secretion levels / increased pain / increased temperature around the incision / tissue necrosis / local erythema / oedema / purulent drainage / dehiscence / odour / other).
- Assessment of incision complications (None / Superficial Infection (i.e. Cellulitis) / Deep Infection /
 Organ/Space Infection / Oedematous / Seroma/ Haematoma / Abscess / Skin Necrosis Partial Dehiscence
 / Total Dehiscence/ Superficial Dehiscence / Deep Dehiscence / Suture Abscess or Extrusions / Delayed
 Healing / Discolouration / Unexpected pain/tenderness/Abnormal smell / Wound breakdown / Other).
- Additional procedures performed (None / Debridement / Removal of Sutures (or clips) / Opening of incision
 / Drainage of incision infection / Antibiotics Oral / Antibiotics Intravenous / Re-suture of incision / I /
 Evacuation of hematoma / Seroma Aspiration / Incision of an Abscess / Debridement / Treatment changed

CONFIDENTIAL AND PROPRIETARY

Study Protocol—Device	Smith-Nephew
and performance of PICO 14 in the	Number: PICO14.WND.PRO.2019.03
	Version: 2.0, 12Sep2021 Page: Page 69 of 131

/ Other. If treatment changed, A different NPWT system / Absorbent dressing / Antimicrobial dressing / other).

- Incision relief (normal / flat / raised).
- Incision colour (pale / white / pink / red / purple / mix).
- Level of itching from the incision (none / slight / moderate / severe).

Question asked at assessments from Treatment Discontinuation to Day 30 for each incision

List any dressings that have been applied to the incision since the previous assessment (None / Steri-strips / Foam dressing / Films/polymer dressing / Alginate/Hydrofiber/ Antimicrobial dressings (silver/iodine) / Hydrocolloid / Non-adherent dressing / Odour absorbent dressing / Absorbent pads / Bandages / Hydrogels / Gauze / Other).

9.2.2 ASSESSMENT OF PERI-WOUND SKIN.

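### Section 9.2.1 gives two conflicting infection definitions for closed incisions, so delayed healing or discoloration alone could be counted as an SSI

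*Combined protocol and SAP*

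**What the plan says.** **Endpoint.** Section 8.6.2 lists, for closed incisions, "Incidence of Surgical Site Infection (SSI) and incidence of Surgical Site Complication (SSC) within 30 days of surgery [CDC criteria". The objective in 5.2 reads "Incidence of Surgical Site Infection (SSI) Superficial, deep. [CDC criteria". The endpoint lists in the synopsis (section 2) and in 11.6 carry the same CDC label.

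**Assessment.** Section 9.2.1 first states: "Assessment of incision infection will be completed as specified per the CDC definitions of nosocomial surgical site infections", to identify superficial, deep or organ/space infection. The sentence that follows defines infection as "the presence of one or more of the following criteria; abscess, cellulites, discharge" and continues, after types of discharge, with "delayed healing, discoloration, unexpected pain/tenderness/bridging of the epithelium or soft tissue, abnormal smell, or wound breakdown". It is credited to a separate publication, not to CDC. One paragraph earlier: "Delayed wound healing would be defined as an incision that is not closed", or that has unhealed parts, beyond 7 days.

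**Data capture.** Section 9.2.1 lists three relevant CRF items:
- A yes/no item: "Incision clinically infected (Yes / No. If yes, deep or superficial infection". It is set out beneath a 'no' answer to whether the incision is closed.
- A list of clinical signs of infection, which contains neither delayed healing nor discoloration.
- An assessment of incision complications. It offers superficial, deep and organ/space infection as options and, separately, delayed healing and "Discolouration / Unexpected pain/tenderness/Abnormal smell / Wound breakdown".

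The complication types for unscheduled visits in 9.1.7 keep the same separation.

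**Analysis.** Section 11.6 makes SSI and SSC binary variables, reported as frequencies and percentages. It gives no rule for setting either to 1.

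**The concern.** The paragraph in 9.2.1 that should fix the case definition gives two, and they differ in kind. One is the external standard named for the endpoint. The other is a low threshold at which a single sign is enough, and at least two of the qualifying signs are treated elsewhere in the protocol as something other than infection. No order of precedence is stated.

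The same incision could then be a non-infective complication to one assessor and an SSI to another. The closed-incision cohort is small and has no comparator, so a few such classifications would change the reported SSI percentage visibly. Under 5.5, the study data go into the clinical evaluation report and support the post-market follow-up plan. A reader of that report could not tell which definition produced the rate.

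**Working it through.** The documents give no expected SSI rate and no SSI sample size, so there is no figure to reproduce. The check has two parts: a comparison of the texts, and an illustration of sensitivity.

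**1. Texts side by side**

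| Place | Delayed healing alone | Discoloration alone |
|---|---|---|
| 9.2.1, CDC sentence | Not decided in the protocol (CDC text not reproduced) | Not decided in the protocol |
| 9.2.1, second definition | Infection | Infection |
| 9.2.1, clinical signs of infection | Not listed | Not listed |
| 9.2.1, incision complications | Own option, apart from the three infection options | Own option, apart from the three infection options |
| 9.1.7, complication types | Own option, apart from infection | Own option, apart from infection |
| 11.6, SSI variable | No rule | No rule |

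The conflict shows without the CDC text: the second definition calls infection what the protocol's own lists record as something else.

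**2. A literal case.** At the Day 14 visit an incision has one small unhealed part and no other finding. It is past 7 days, so it meets the delayed-healing definition. Delayed healing is on the one-or-more list, so the second sentence of 9.2.1 makes it infected. On the complications item, the same incision would be ticked as delayed healing and not under any infection option.

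**3. Which item would feed SSI.** There are two candidates. The clinically-infected item is asked, as laid out, only when the incision is not closed, and it offers only deep or superficial. The complications item is not conditional on closure and includes organ/space. The two can disagree, and 11.6 chooses neither.

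**4. Sensitivity of the rate.** Inputs from 7.1: 70 patients and a minimum of 10 in each of five wound types.

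- Minimum number of closed incisions: 10.
- Maximum, if the other four types stay at 10 each: 70 − 4 × 10 = 30.
- Effect of one reclassified incision: 1/10 = 10 percentage points; 1/30 = 3.3 points.

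The exact (Clopper-Pearson) 95% interval for k events in n has lower limit Beta(0.025; k, n − k + 1) and upper limit Beta(0.975; k + 1, n − k). The lower limit is 0 when k = 0, and the upper limit is then 1 − 0.025^(1/n).

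| Assumed reclassified incisions | n = 10 | n = 30 |
|---|---|---|
| 0 | 0% (0 to 30.8%) | 0% (0 to 11.6%) |
| 1 | 10% (0.3 to 44.5%) | 3.3% (0.1 to 17.2%) |
| 2 | 20% (2.5 to 55.6%) | 6.7% (0.8 to 22.1%) |

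The counts are assumptions. The documents do not say how many incisions will show delayed healing or discoloration alone.

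**The case against.** The best defence is that CDC governs in practice. Every statement of the SSI endpoint carries the CDC label, the heading of 9.2.1 refers to CDC assessment, and the wider sentence defines infection without using the term SSI. The CRF keeps infection apart from delayed healing and discoloration, and nothing in 11.6 converts a delayed-healing tick into an SSI. The assessor is medically qualified and must have no vested interest in low reporting, sites are trained to standardise the assessment, and section 11 promises a more detailed SAP before database lock.

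Much of this stands as mitigation. It does not settle precedence: training needs one rule to teach and the protocol supplies two. A later SAP can choose a field, but it cannot undo entries that sites made under different rules.

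The defence does limit what can be claimed. A reader might infer more on four counts:

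- **That such incisions will be counted as SSI.** The text supports only that they could be, if an assessor applies the second sentence literally.
- **That every non-specific sign on the list is shown to be non-infective.** Section 4.2 names exudate and superficial dehiscence as SSI features, and the clinical-signs list in 9.2.1 includes increased pain, odour and dehiscence. The internal contrast is clear only for delayed healing and discoloration.
- **That the rate loses comparability with CDC-based rates in the background.** Section 4.2 does not say which criteria its SSI rates used.
- **That a main safety endpoint is affected.** SSI and SSC form one of eleven closed-incision secondary bullets in 8.6.2 and are analysed descriptively. The designated safety endpoints in 8.6.4 are adverse events and device deficiencies.

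**Conclusion.** The point holds as an internal inconsistency that should be corrected. Section 9.2.1 states two infection definitions that can classify the same closed incision differently, and neither 9.2.1 nor 11.6 says which one sets the SSI variable. An incision with delayed healing or discoloration and nothing else could be counted as an SSI.

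Each such incision moves the SSI rate by between 3.3 and 10 percentage points, for 30 and 10 closed incisions respectively. This rests on the recruitment figures in 7.1 and on assumed counts, so it shows sensitivity and does not predict a bias. The primary endpoint and the sample size are not affected.

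**What to change.** - **9.2.1:** State that the CDC criteria are the sole definition for the SSI endpoint. Keep the wider list only as recorded clinical signs, and summarise it in a separate table. Do not move these signs into SSC: the SSC list in 5.2 names dehiscence, seroma, necrosis, hematoma and suture abscess, and adding to it would change a second endpoint.
- **11.6:** State that SSI = 1 is set from the superficial, deep or organ/space infection options of the incision-complications item, completed by the CDC criteria. The clinically-infected item is unsuitable as the source because it is asked only when the incision is not closed and has no organ/space option.
- **Training:** Teach this one rule in the assessor session already planned in 9.2.1.

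The cost is a few sentences in two sections. The named item is already on the CRF, so no new data item is needed. If any incision has been assessed before the change, its infection entry should be checked against the single definition.
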